9.4.2. INTENT

A subject who signs informed consent, meets key eligibility criteria, but does not have any study devices inserted into the body will be classified as “INTENT.” For prospectively enrolled subjects that are enrolled in the study but do not undergo ablation procedure within 30 days from consent signature date must not be reconsented and will be withdrawn from the study and classified as “INTENT.” These subjects won’t be allowed to be re-enrolled in the study.

There are no follow-up requirements for INTENT subjects. INTENT subjects will not count for analysis of the endpoints and do not count toward the enrollment ceiling. The original signed ICF must be maintained in the center’s patient file. A subject ID will be assigned in the EDC system.

For INTENT subjects, at the minimum the following forms must be completed:

- Enrollment and baseline forms such as, but not limited to informed consent, enrollment information and other related forms.
- End of Study form;
- Adverse Event forms for any reportable event, as defined in **Section 18.1** for any adverse event that occurs after signing the Informed Consent, up to the point of subject withdrawal

9.4.3. ATTEMPT

An ATTEMPT subject is one who signs informed consent, meets eligibility criteria, and has any study device inserted into the body but does not receive ablation (PFA energy) with the FARAPULSE Pulsed Field Ablation System for PVI. ATTEMPT subjects will be used for analysis of the primary and secondary safety endpoints and count toward the enrollment ceiling.

The original signed Informed Consent and any relevant documentation must be maintained in the site’s subject file. A subject ID will be assigned in the EDC system. ATTEMPT subjects are not allowed to be re-enrolled in the study.

Prospectively enrolled ATTEMPT subjects will be followed up to 30 days for safety. For

retrospectively enrolled ATTEMPT subjects, one-month follow-up data will be collected. ATTEMPT subjects will not need to complete data collection of the post-procedure arrhythmia. All applicable eCRFs, per the protocol, will be completed.

For ATTEMPT subjects, at the minimum the following forms must be completed:

- Enrollment and baseline forms such as, but not limited to: ICF, enrollment information and other related forms.
- End of Study form.
- Protocol Deviation form
- Adverse Event forms for any reportable event, as defined in Section 18.1 for any adverse event that occurs after signing the ICF, up to the point of subject withdrawal

9.4.4. *TREATMENT*

Any subject that signs the ICF, meets key eligibility criteria and has the specified study device inserted into the body and receives PFA ablation with the FARAPULSE Pulsed Field Ablation system will be classified as “TREATMENT”. The data collection of these subjects will be performed in accordance with the follow-up schedule and are included in all study analyses. A subject ID will be assigned in the EDC system.

All applicable eCRFs, per the protocol, must be completed for TREATMENT subjects. TREATMENT subjects do count towards the enrollment ceiling and will be used for analyses of the endpoints. The original signed ICF and any relevant documentation must be maintained in the center’s patient file.

9.5. *End-of-Study Definition*

A clinical trial is considered completed when the last participant’s last study data collection has occurred.

A subject is considered to have completed the study if he/she has completed all data collection including the last visit or assessment as shown in the Data Collection Schedule shown in **Table 10-1**.

The end of the study is defined as completion of data collection shown in the Data Collection Schedule including the 12-month follow-up visit.

9.6. *End of Study Action Plan*

This is a real-world study. All the subjects will continue to accept routine follow-up under standard of care.

10. Study Methods

10.1. *Data Collection*

The data collection schedule is shown in **Table 10.1-1**.

Table 10.1-1 Data Collection Schedule

Data Collection	Baseline Visit Clinic Visit	Procedure Visit (Day 0) Clinic Visit	Follow-up (FU) Visits					
			7 days FU (7-10 days) Telephone interview	1 M FU (30±7 Days) Telephone interview	3 M FU (91-104 Days) Clinic Visit	6 M FU (180±30 Days) Clinic Visit	12 M FU (365±30 Days) Clinic Visit	Unscheduled FU Clinic Visit
Informed consent	X							
Baseline information including demographics information	X							
Eligibility Criteria	X							
Pregnancy test	X ¹							
Medical history	X							
Physical Assessment	X							
Related Blood Tests	X							
Transthoracic echocardiogram (TTE)	X ²							
Cardiac CT/MRI	X ³		X ³	X ³	X ³	X ³	X ³	X ³
TEE/ICE to exclude LA thrombus	X ⁴	X ⁴						
Procedural Data		X						
Phrenic Nerve Palsy Assessment		X	X ⁵	X ⁵	X ⁵	X ⁵	X ⁵	X ⁵
AF Symptom Assessment	X						X	
AADs and anticoagulant medications	X	X	X	X	X	X	X	X
Documentation of intervention AF/AFL/AT			X	X	X	X	X	X

12-lead ECG	X ⁷				X	X	X	X ⁷
24h Holter	X ⁷				X ⁷	X	X	X ⁷
Neuro assessment	X ⁶							
Adverse events	X	X	X	X	X	X	X	X
Device Deficiency Assessment		X	X	X	X	X	X	X
Protocol Deviations	X	X	X	X	X	X	X	X

¹ Females of childbearing potential.

² TTE obtained \leq 6 months prior to procedure will be acceptable, unless a cardiac event has occurred (e.g., MI, acute heart failure or acute onset heart failure) between the date of the exam and the procedure. In this case, a new TTE is needed. The most recent report before the procedure will be used.

³ Cardiac CT/MRI obtained \leq 3 months prior to procedure will be acceptable. Cardiac CT/MRI scan may be considered post-procedure if PV stenosis is suspected at the physician's discretion.

⁴ The absence of thrombus must be confirmed by means of a trans-esophageal echocardiogram (TEE) within 48 hours prior to the procedure or Intracardiac Echography (ICE) during the procedure.

⁵ Phrenic Nerve Palsy Assessment at discharge and at follow-up visits is only applicable for subjects who had phrenic nerve palsy detected during the index or repeat procedure. Subjects should be assessed per standard of care; suggested means of assessment include a sniff test or an inhalation-exhalation chest radiography of the diaphragm.

⁶ If there is a clinical suspicion of stroke/TIA by the physician, then the data of neuro assessment, including but not limited to specialist consultation and brain MRI, will be collected.

⁷ Collect results if applicable, the absent of this assessment is not Protocol Deviation.

10.2. Study Candidate Screening

Investigators are responsible for screening all subjects and selecting those who are appropriate for study inclusion. The investigator is expected to follow standard of care testing to diagnose and screen subjects for inclusion in the study. A Screening and Enrollment Log will be maintained to document select information about candidates who fail to meet the general and specific selection criteria, including those enrolled in the study and classified either as Screen Failure, INTENT, ATTEMPT or TREATMENT subjects.

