Component Name	Model																																												
FARASTAR Pulsed Field Ablation Generator System																																													
FARASTAR Pulsed Field Ablation Generator	61M401																																												
FARASTAR Recording System Module (RSM)	61M407																																												
FARASTAR Stimulation Module Cable	61M404																																												
FARASTAR EGM Cable	61M405																																												
FARASTAR Stimulation Module Auxiliary Cable	61M408																																												
FARASTAR Cable Set	61M406																																												
FARASTAR Stimulation Module Male Cable	61M409																																												
FARASTAR Stimulation Module Female Cable	61M410																																												
FARASTAR Stimulation Module Y-Cable, Long	61M411																																												
FARASTAR Stimulation Module Y-Cable, Short	61M412																																												
FARASTAR Recording System Module Catheter Pin Cable	61M413																																												
FARASTAR Recording System Module ECG Trunk Cable	61M415																																												
FARASTAR Recording System Module ECG Output Module	61M416																																												
FARASTAR Recording System Module EGM Input Module	61M417																																												
FARAWAVE Pulsed Field Ablation Catheter																																													
FARAWAVE Pulsed Field Ablation Catheter, 35mm	41M402																																												
FARAWAVE Pulsed Field Ablation Catheter, 31mm	41M401																																												
FARASTAR Catheter Connection Cable	41M404																																												
FARADRIVE Steerable Sheath																																													
FARADRIVE Steerable Sheath	21M402																																												
Study Design	This is a retrospective and/or prospective single-center single-arm observational study.																																												

A Real-world Study of the FARAPULSE Pulsed Field Ablation System in A Chinese Population with Paroxysmal Atrial Fibrillation (REPLACE Study)

Planned Number of Subjects	At least 30 ATTEMPT and TREATMENT subjects
Planned Number of Sites / Countries	1 site

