**TTE obtained ≤ 6 months prior to procedure will be acceptable, unless a cardiac event has occurred (e.g. MI, acute heart failure or acute onset heart failure) between the date of the exam and the procedure. In this case, a new TTE is needed to confirm eligibility for mITT. The most recent report before the procedure will be used. LA anteroposterior diameter measured by M-mode from the parasternal long-axis view will be used.*

#The absence of thrombus must be confirmed by means of a trans-esophageal echocardiogram (TEE) within 48 hours prior to the procedure or Intracardiac Echography (ICE) during the procedure.

^Y Cardiac CT/MRI obtained ≤ 3 months prior to procedure will be acceptable.

Statistical Methods

Primary Statistical Hypothesis	There are no formal hypotheses testing in this small sample size observational study.
Statistical Test Method	
Descriptive statistics will be conducted for the endpoint events. Explorative statistical analysis might be produced if appropriate, such as Bayesian estimation of the study results using ADVENT data as the prior.
 
Primary effectiveness endpoints will be summarized for TREATMENT subjects in modified Intent-to-Treat (mITT) set.
 
Secondary effectiveness endpoints will be summarized for TREATMENT subjects in Intent-to-Treat (ITT) set and mITT set respectively.
 
Primary and secondary safety endpoints will be summarized for ATTEMPT and TREATMENT subjects in ITT set.
 
The additional endpoints will be summarized for TREATMENT subjects in ITT set.

Sample Size Parameters	No formal sample size calculation is performed because there is no

A Real-world Study of the FARAPULSE Pulsed Field Ablation System in A Chinese Population with Paroxysmal Atrial Fibrillation
(REPLACE Study)

formal hypothesis testing in the study. The following table provides a 95% confidence interval (exact methods) for a sample size of 30 if there are 0 ~ 3 primary safety events.

Events	Rates (n=30)	Lower 95%CI	Upper 95%CI
0	0%	0%	11.6%
1	3.3%	0.1%	17.2%
2	6.7%	0.8%	22.1%
3	10%	2.1%	26.5%

3. Table of Contents

1. COVER PAGE	1
2. PROTOCOL SYNOPSIS.....	4
3. TABLE OF CONTENTS.....	19
3.1. Table of Figures.....	24
3.2. Table of Tables	24
4. INTRODUCTION	25
4.1. Background.....	25
4.1.1. Background and Rationale	25
4.1.2. Irreversible Electroporation	25
4.1.3. Summary of Clinical Studies about FARAPULSE Pulsed Field Ablation System used for PAF	26
4.2. Study Rationale	30

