6.2.2.2. Secondary Safety Endpoints

Proportion of subjects that free from primary safety events defined as above through 7 days after the procedure and free from the following serious procedure-related and/or device-related adverse events at any time through the completion of 12-month follow-up visit. based on the definitions contained in **Table 6.2-1**.

- Atrial oesophageal fistula
- Severe PV stenosis
- Persistent phrenic nerve palsy*

**The study will collect information on phrenic nerve palsy observed before the end of the index procedure and, in case of occurrence, will track information for potential recovery during the study visits*

6.2.3. *Other Endpoints*

1. AF Symptom Assessment: AF symptoms will be assessed at baseline and 12 months.
2. Procedural parameters:
 - Total procedure time (initiation of venous access to venous access closure)
 - Left atrial dwell time (total time an ablation catheter is in the left atrium [LA])
 - Total PVI ablation time (first ablation to last ablation for PVI)
 - Fluoroscopy time (total duration of exposure)

[figure not shown]
7. Study Design

The REPLACE study is a retrospective and/or prospective single-center single-arm observational real-world study to observe the safety and effectiveness of the FARAPULSE Pulsed Field Ablation system for treatment of recurrent, symptomatic PAF in a Chinese population in the real world. Primary endpoints analysis is planned to be conducted after all enrolled subjects have completed data collection at 1-month follow-up visit. All the subjects underwent study device treatment will be followed up to 12 months after the procedure, and the secondary and other endpoints will be analyzed then. The final report will be completed then too.

7.1. *Scale and Duration*

Thirty ATTEMPT and TREATMENT subjects will be enrolled in this study. The enrollment period for this study is expected up to 6 months depending on the precent of patients enrolled prospectively. Each subject will be followed under standard of care after the ablation procedure with a follow-up duration of 12 months. The study duration is estimated up to 18 months. Primary endpoints analysis is planned to be conducted after all enrolled subjects have completed data collection at 1-month follow-up visit. All the subjects underwent study device treatment will be followed up to 12 months after the procedure, and the secondary and other endpoints will be analyzed then. The final report will be completed then too.

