7.4. Method to control biases

This is a real-world study. Selection of patients will be made from the Investigational site's routine patients. All patients meeting the key eligibility criteria and having signed the ICF will be eligible for enrollment in the study. Control and reduction of potential bias associated with

a single-arm study design have been taken into account by defining key inclusion and exclusion criteria to represent a population similar to the patients with AF ablation in the real world, and defining a mITT set with population similar to the subjects enrolled in ongoing ADVENT trial and other trial about AF ablation.

Every effort will be undertaken to minimize missing or incorrect data. However, some missingness is inevitable. The reasons for missing or incorrect data will be described in detail and evaluated for assessment of possible bias if appropriate.

8. Subject Selection

8.1. *Study Population and Eligibility*

Subjects enrolled in the REPLACE study will be clinically indicated for an ablation procedure for the treatment of symptomatic, recurrent PAF with Class I or IIa recommendations according to 2018 Chinese expert consensus statement on atrial fibrillation therapy. Subjects must meet the key inclusion/exclusion criteria as outlined below in **Section 8.2** and **8.3**. Subjects assigned to modified ITT set must meet all the key criteria and additional criteria as outlined below in **Section 8.3**. The subjects selected for participation will be from the investigational site's general patient population. The investigator or its designee has the responsibility for screening all potential subjects and selecting those who meet study eligibility criteria.

8.2. *Inclusion Criteria*

Subjects who meet all of the following criteria (see **Table 8.2-1**) may be given consideration for inclusion in this clinical investigation, provided no exclusion criterion (see **Section 8.3**) is met.

Table 8.2-1: Inclusion Criteria

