Key Inclusion Criteria	
1. Subjects who are ≥ 18 and ≤ 75 years of age on the day of enrollment;2. Subjects whose preoperative diagnosis is PAF confirmed by the clinician;3. De novo ablation procedure for PAF with Class I or IIa recommendations* according to 2018 Chinese expert consensus on atrial fibrillation therapy;4. Subjects who are able and willing to provide the defined observational data and/or participate in baseline and follow-up evaluations for the full study;5. Subjects who are willing and capable of providing informed consent. 
* In 2018 Chinese expert consensus on atrial fibrillation therapy, subjects with recurrent, symptomatic PAF and refractory or intolerant to at least one class I or class III antiarrhythmic medication are recommended to accept ablation therapy under Class I recommendation; Subjects with recurrent, symptomatic PAF are recommended to accept ablation therapy as the first line therapy under Class IIa recommendation.

-------------------------------	--

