11.2.2. Control of Systematic Error/Bias

This is a real-world study. Selection of patients will be made from the Investigational site's routine patients. All patients meeting the key eligibility criteria and having signed the ICF will be eligible for enrollment in the study. Control and reduction of potential bias associated with a single-arm study design have been taken into account by defining key inclusion and exclusion criteria to represent a population similar to the patients with AF ablation in the real world and defining a mITT group with population similar to the subjects enrolled in ongoing ADVENT trial and other trials about AF ablation.

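### Retrospective subjects can be chosen after their outcomes are on record, and no consecutive-enrolment rule or check against the procedure list protects the two primary rates

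*Protocol*

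**What the plan says.** The Synopsis gives the design: "This is a retrospective and/or prospective single-center single-arm observational study". No section caps or fixes the retrospective share. Protocol 7.1 states the size: "Thirty ATTEMPT and TREATMENT subjects will be enrolled in this study"; the Synopsis puts it as a minimum of 30. The analysis is descriptive, with exact 95% intervals.

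On who enters, 10.2 says "Investigators are responsible for screening all subjects and selecting those who are appropriate for study inclusion", and 8.1 says "The investigator or its designee has the responsibility for screening all potential subjects and selecting those who meet study eligibility criteria". The bias sections (Protocol 7.4 and 11.2.2, SAP 4.2) say "Selection of patients will be made from the Investigational site's routine patients" and "All patients meeting the key eligibility criteria and having signed the ICF will be eligible for enrollment in the study". Beyond that they rely on the eligibility criteria and the mITT set.

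On timing, for retrospectively enrolled subjects 10.5 allows procedure data to be collected on the same day as baseline data. Sections 10.6 to 10.10 extend this visit by visit to 12 months.

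On the log, 9.1 requires eligibility to be assessed before consent and documented for each screened patient, and 9.4 requires all screened subjects to be listed. Section 10.2 is narrower: it mentions candidates who fail criteria and those enrolled.

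**The concern.** The study has one arm, one centre and no comparator. Protocol 4.2 and 7.3 say that its data are meant to support registration in China. The rates can be read as describing patients treated with the device only if the enrolled subjects represent all patients treated.

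For prospective subjects the outcome does not exist when they are chosen. For retrospective subjects the order is reversed: the procedure is done, its result is recorded, and only then is the patient screened and asked for consent. Sections 9.1 and 10.3 forbid study data collection before consent, but the outcome is already in the hospital's own records. The bias text says who may be enrolled. It does not say who must be approached. The site can therefore follow the plan exactly while the retrospective subjects are a non-random subset of those treated.

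Consent adds a route that needs no intent. Key inclusion 5 requires each subject to be able and willing to consent. Sections 10.3 and 19 allow a legal representative, and Section 19 lets a consenting subject name someone to respond after the subject's death. Neither covers a patient who died before being asked. Death is the first component of the primary safety endpoint.

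**Working it through.** **1. The plan's own figure.** Protocol 11.1.1.1.2 and SAP 3.2.2 tabulate exact 95% intervals for 0 to 3 events in 30. Two-sided Clopper-Pearson limits reproduce every row: 0% (0 to 11.6), 3.3% (0.1 to 17.2), 6.7% (0.8 to 22.1) and 10% (2.1 to 26.5). For 0/30 the upper limit is 1 − 0.025^(1/30) = 11.6%.

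**2. What is known at retrospective enrolment.** The acute isolation result exists once the procedure is over. The 7-day and 12-month outcomes exist if enough time has passed, and the same-day collection in 10.6 to 10.10 shows that the plan expects such cases.

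**3. What the log would show.** A patient who is screened, found eligible and not enrolled should appear under 9.1 and 9.4, but without a required reason. A treated patient who is never screened need not appear, because no section defines screening by reference to the procedures performed.

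**4. Effect of restoring omitted patients.** Suppose 0 events in 30 were reported and k event patients had been passed over. The complete series is k/(30 + k). The success column does the same for k acute failures, taking all 30 subjects as mITT.

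| k | Safety event rate (95% CI) | Acute success (95% CI) |
|---|---|---|
| 0 | 0/30 = 0% (0 to 11.6) | 30/30 = 100% (88.4 to 100) |
| 1 | 1/31 = 3.2% (0.1 to 16.7) | 30/31 = 96.8% (83.3 to 99.9) |
| 2 | 2/32 = 6.3% (0.8 to 20.8) | 30/32 = 93.8% (79.2 to 99.2) |
| 3 | 3/33 = 9.1% (1.9 to 24.3) | 30/33 = 90.9% (75.7 to 98.1) |

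**5. Chance of a clean safety result.** Two rates in Protocol 4.1 serve as illustrations: p = 2.5% (3/121, the pooled earlier studies of this device, with a 7-day or 30-day window depending on the study) and p = 6.29% (complications of radiofrequency ablation). Without selection, P(0 in 30) = (1 − p)^30:
- 0.975^30 = 0.47
- 0.9371^30 = 0.14

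Let m of the 30 be retrospective, and let q be the chance that a retrospective event patient is passed over. Neither m nor q is in the documents; both are assumed. Then P(0 in 30) = (1 − p)^(30 − m) × [(1 − p)/(1 − pq)]^m. For m = 15 and q = 1 this is 0.975^15 = 0.68 and 0.9371^15 = 0.38.

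| m | p = 2.5%, q = 0.5 | p = 2.5%, q = 1 | p = 6.29%, q = 0.5 | p = 6.29%, q = 1 |
|---|---|---|---|---|
| 8 | 0.52 | 0.57 | 0.18 | 0.24 |
| 15 | 0.57 | 0.68 | 0.23 | 0.38 |
| 22 | 0.62 | 0.82 | 0.29 | 0.60 |
| 30 | 0.68 | 1 | 0.37 | 1 |

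**6. Expected reported rate.** With retrospective share r = m/30, this is (1 − r)p + r·p(1 − q)/(1 − pq). At r = 0.5 and q = 1, 2.5% becomes 1.25% and 6.29% becomes 3.15%. At q = 0.5 they become 1.88% and 4.77%.

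**The case against.** The best defence is that the plan ties selection to eligibility. Section 8.1 says so directly, and 10.2 speaks of screening all subjects. A reader might infer from 10.2 that the plan instructs free choice by the investigator. Read with 8.1, it does not: passing over an eligible patient because of an event is not something the plan directs. This stands, so the defect is a missing safeguard. But eligibility does not settle which eligible patients are approached.

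A reader might also infer that eligible patients passed over are never logged. Sections 9.1 and 9.4 contradict that for anyone screened. What remains is narrower: treated patients who are not screened, the absence of a recorded reason, and the narrower wording in 10.2.

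Nor are 7-day events necessarily known at retrospective enrolment. The term is not defined by time since procedure, and 10.8 allows for subjects followed up prospectively, so a subject could be consented before day 7.

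Key inclusion 4, "Subjects who are able and willing to provide the defined observational data and/or participate in baseline and follow-up evaluations for the full study", might be read as favouring patients with complete records. It applies to everyone and does not demand completeness. Sections 10.5.2 and 12.3 tolerate retrospective gaps, and 11.2.3 provides for missing data.

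On size, Protocol 4.1.3 reports 100% acute success in the earlier trials. If that held here, there would be few failures to omit, so the exposure is mainly on safety.

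Finally, Protocol 11.3.5 and SAP 5.3 already split the primary and secondary endpoints by prospective enrolment. The split could hint at a difference, but it is imprecise when 30 subjects are divided, and it cannot recover patients who were never enrolled.

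**Conclusion.** The concern holds as a gap in bias control for the retrospective part. The plan can be followed to the letter while retrospective subjects are chosen with the acute result, and possibly the 7-day and 12-month outcomes, on record. Neither the sponsor nor a regulator could then show that the enrolled subjects represent all those treated.

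The two-patient case illustrates the size: the safety estimate moves by about 6 percentage points, and the upper limit goes from 11.6% to 20.8%. The rise from 0.47 to 0.68 assumes a 2.5% event rate, half the subjects retrospective and every retrospective event patient passed over. Milder assumptions give smaller shifts, and with no retrospective subjects there is none.

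The documents permit selection. They do not show that it occurred or was intended. The 12-month endpoints are exposed in the same way, but no size can be given because the documents do not say how many eligible patients were treated.

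**What to change.** Amend Protocol 7.4, 10.2 and 11.2.2 and SAP 4.2, for the retrospective part only, since prospective subjects consent before the procedure (10.3):

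- List all patients treated with the FARAPULSE system at the site from a fixed start date, in order of procedure date. Approach all eligible ones consecutively until at least 30 ATTEMPT or TREATMENT subjects are enrolled in the study.
- Record every treated patient on that list in the Screening and Enrollment Log, with the reason if not enrolled, including death before consent. Align the description in 10.2 with 9.1 and 9.4.
- Reconcile the log with the site's procedure list.
- Report a flow table from treated to analysed patients, and beside it both primary rates by prospective and retrospective enrolment. The split itself is already planned.

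If enrolment has closed, the list and the reconciliation can still be made from site records and reported, though the order of approach cannot be changed.

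The cost is wording and a fuller log at one centre, with no extra patients or procedures. The rates may look slightly less favourable.
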